**Table 3: Comprehensive List of Anticipated Adverse Events**

Anticipated Adverse Events	
(Acute) renal failure	Infection, systemic
(Aspiration) pneumonia	Inflammation
(Skin) laceration	Isolated ST segment elevation
(Vascular) bleeding	Liver toxicity
Acute Respiratory Distress Syndrome (ARDS)	Local Hematoma/ecchymosis
Air embolism	Localized skin reaction
Allergic reaction to contrast media	Mitral Insufficiency
Allergic skin reaction	Myocardial infarction with or without ST elevation
Altered Mental Status Confusion; Altered Level of Consciousness;	Nausea
Anaphylactic shock	Neurological disorders (poor coordination)
Anemia	Neurological disorders (tremor)
Anesthesia complications/reactions	Neuropraxia/Muscle contraction
Anoxic or hypoxic encephalopathy	Palpitations
Aortic Puncture	Papillary Muscle tear/injury
Apnea - sedation induced	Pericardial effusion resulting in tamponade
Arrhythmia (new or worsening of pre-existing arrhythmia)	Pericardial effusion without tamponade
Asthmatic attack	Pericarditis
Asymptomatic Cerebral Emboli	Periesophageal vagal nerve injury
Atelectasis	Peripheral nerve injury
Atrial fibrillation	Phlebitis
Atrial Septal Defect (acquired)	Phrenic nerve damage/injury
Atrio-Esophageal fistula	Pleural effusion
Auditory Disorder	Pneumothorax
AV fistula	Post- and perioperative pain
Back Pain	Post Procedural Hematuria
Bone disorder	Pseudoaneurysm
Bronchial fistula, Broncho-pericardium fistula	Pulmonary edema
Cardiac arrest	Pulmonary embolism
Cardiac pacemaker insertion or replacement	Pulmonary hypertension
Cardiac perforation	Pulmonary toxicity, like acute pulmonary syndrome
Cardiac Valve Rupture/Damage	Pulmonary vein dissection
Cardiogenic Shock	Pulmonary vein stenosis
Cerebro-Vascular accident (CVA)/Stroke	Renal Artery Stenosis
Chest pain/discomfort	Respiratory arrest
Complete or incomplete heart block	Respiratory depression
Conduction block	Respiratory failure
Coronary Artery Stenosis	Respiratory infection
Coronary artery thrombosis	Retinal Artery Embolism
Death	Retroperitoneal bleeding

Deep venous thrombosis	Rhabdomyolysis, including produced by body position or propofol
Diaphragmatic paralysis	Sedation induced CO 2 retention with lethargy and cholecystitis
Dislodgement/Malfunction of pacemaker/defibrillator leads	Seizure
Disseminated Intravascular Coagulation	Sepsis
Dizziness, presyncope, vertigo	Sinus bradycardia
Dysphagia	Sinus tachycardia
Dyspnea	Skin burn or necrosis
Endocarditis	Skin discoloration
Epigastric Distress	Skin edema
Epistaxis	Skin or soft tissue (radiation) injury/tear
Esophageal injury / perforation	Subclavian artery puncture
Expressive aphasia	Temperature elevation / Fever
Fatigue	Thrombocytopenia
Gastric hypomotility	Thromboembolism
Gastroesophageal reflux	Thrombosis
Gastrointestinal disorders	Thyroid disorders
Gastrointestinal diverticulosis	Toxic reaction
Gastroparesis	Transient extremity numbness
Headache	Transient Ischemic attack (TIA)
Heart failure (acute or chronic)	Urinary Retention Postoperative
Heart injury	Urinary tract injury or infection related to the urinary catheter
Heart valve insufficiency	Valvular damage/insufficiency
Hemoptysis	Vascular (access) dissection (including coronary arteries)
Hemorrhage	Vascular occlusion
Hemothorax	Vasovagal reactions
High/increased creatine phosphokinase (CPK)	Ventricular Fibrillation
Hypertension	Vessel damage/trauma
Hypervolemia	Vessel perforation
Hypotension	Vessel spasm (including coronary arteries)
Hypovolemia	Visual disturbance
Hypoxia	Worsening of pre-existing pulmonary disease
Increased phosphokinase level	Wound healing disturbance
Infection, localized	

\*Atrial Fibrillation and exacerbation of an existing arrhythmia are anticipated adverse events. However, they will not be captured as such under this protocol, as they are considered recurrence of disease.

NA	Neurological Assessment
NIHSS	National Institute of Health Stroke Scale
NSC	Non-Study Catheter
PAE	Primary Adverse Event
PAF	Paroxysmal Atrial Fibrillation
PEE	Primary Effectiveness Endpoint
PF energy	Pulsed Electric Field Energy
PP	Per Protocol
PV	Pulmonary Vein
PVI	Pulmonary Vein Isolation
QoL	Quality of Life
RF	Radiofrequency
SADE	Serious Adverse Device Effect
SAE	Serious Adverse Event

Acronym/ Abbreviation	Expanded Term
SAP	Statistical Analysis Plan
USADE	Unanticipated Serious Adverse Device Effect

Table of Contents

1	Study Design	9
2	Treatment Assignment	10
3	Randomization and Blinding Procedures	10
4	Levels of Significance	10
5	Analysis Sets	10
	5.1 Main Study	10
	5.2 Roll-In	11
6	Sample Size Justification	11
7	Statistical Analysis Methods	12
	7.1 General Conventions	12
	CCI	12
	7.2 Disposition of Study Subjects	15
	7.3 Demographic and Baseline Characteristics	15
	7.4 Endpoints and Associated Hypotheses	15
	7.4.1 Primary Safety Endpoint	15
	7.4.2 Primary Effectiveness Endpoint	15
	7.4.3 Secondary Effectiveness Endpoint	16
	7.4.4 Additional Endpoints	16
	7.4.5 Additional Effectiveness Endpoints	17
	7.5 Analysis of Primary Endpoints	18
	7.5.1 Primary Safety Endpoint	18
	7.5.2 Criteria for Study Success	20
	7.6 Sensitivity Analyses	20
	7.6.1 Primary Safety Endpoint	20
	7.6.2 Primary Effectiveness Endpoint	21
	7.7 Subgroup Analyses	21
	7.8 Handling of Missing Data	22
	7.8.1 Primary Safety Endpoint	22
	7.8.2 Primary Effectiveness Endpoint	22
	7.8.3 Secondary Effectiveness Endpoint	22
	7.9 Adjustments for Multiplicity	22
	7.10 Analyses of Secondary Endpoints	23
	7.11 Additional Endpoint Analyses	24
	7.11.1 Additional Procedural Endpoints	24
	7.11.2 Additional Safety Endpoints	24
	7.11.3 Additional Effectiveness Endpoints	25
	7.12 Subset Analyses	29
	7.12.1 Analysis of PVI Durability Endpoint	29
	7.12.2 Analysis of NA Endpoint	29
	7.12.3 Analysis of CT/MRA Endpoint	30
	7.12.4 Analysis of EE Endpoint	30
8	Handling of Deviations from Planned Analyses	30
9	Data Monitoring Committee (DMC)	31

10 References 32

1 Study Design

This study is a prospective, multi-center, single-arm, pre-market clinical evaluation utilizing the OMNYPULSE™ Bi-Directional Catheter in conjunction with the guiding sheath and the TRUPULSE™ Generator, for the treatment of symptomatic paroxysmal atrial fibrillation (PAF) with pre-specified goals for safety and effectiveness.

The main study will enroll 135 evaluable subjects who have symptomatic PAF and are candidates for atrial fibrillation ablation. To minimize the learning curve effect on the evaluation of safety and effectiveness of the OMNYPULSE™ Bi-Directional Catheter, up to 50 Roll-In subjects will be enrolled in the study. These subjects will not be counted in the main study, and data for Roll-In subjects will be analyzed separately from the main study.

During the study, all subjects will be followed for 12 months after index procedure. All subjects will be evaluated at 7 days (Day 7-9), 1 month (Day 23-37), 3 months (Day 76-104), 6 months (Day 166-194), and 12 months (Day 335-379) following the index ablation procedure (Day 0).

The primary safety and effectiveness endpoint will be evaluated using the data available at the time of the 3-month follow-up. The hypothesis testing of the primary endpoints will be performed when all subjects complete their 3-month follow-up. A Clinical Study Report (hereinafter, 3-Month CSR) will be submitted as part of the CE mark application dossier.

After the 3-Month CSR submission, the primary safety and primary effectiveness endpoints, along with associated sensitivity analyses, may be summarized descriptively using the complete follow-up data, if there are any updates on the primary endpoint outcome data. No hypothesis testing will be conducted for the primary endpoints in the final CSR.

Regarding all other study endpoints, they will be summarized descriptively using the full follow-up data. The final analysis results will be compiled and presented in the Final CSR (hereinafter, Final CSR).

Embedded within the main study, there will be a Neurological Assessment (NA) subset, a cardiac Computed Tomography (CT) or Magnetic Resonance Angiogram (MRA) image subset, an Esophageal Endoscopy (EE) subset, and a Pulmonary Vein Isolation (PVI) durability subset. These subsets are intended to delineate safety and assess lesion durability 2-3 months following ablation. Each subset will consist of 30 subjects. The same subjects may participate in all four (4) subsets.

2 Treatment Assignment

This is a single-arm study. All subjects will be treated with the OMNYPULSE™ Bi-Directional Catheter (D-1430-05-SI) and the TRUPULSE™ Generator (D-1417-01-IC), along with any related components and accessories needed for the ablation procedure.

3 Randomization and Blinding Procedures

This study is a non-randomized single-arm study. Therefore, masking of treatment assignment for operators and subjects will not be performed. To minimize operational bias, the study will maintain screening logs at each site to ensure that eligible subjects are considered for participation in the study.

4 Levels of Significance

The type-I error rate for the analyses of the two primary endpoints is controlled each at a one-sided 2.5% level. The hypotheses of the primary endpoints will be tested at the full alpha level of 0.025, and only if there is a success, the hypothesis testing of the secondary endpoint will be performed at the same alpha level. This gate-keeping approach will control the overall type-I error rate at a one-sided 2.5%.

5 Analysis Sets

5.1 Main Study

For the analysis of study endpoints, the analysis sets defined in the following will be used:

- **Safety Analysis Set:** CCI [REDACTED]
- **Modified Intent-To-Treat (mITT) Analysis Set:** CCI [REDACTED]
- **Per Protocol (PP) Analysis Set:** CCI [REDACTED]

CCI

- **Neurological Assessment (NA) Analysis Set:** CCI

- **Esophageal Endoscopy (EE) Analysis Set:** CCI

- **Cardiac CT/MRA Analysis Set:** CCI

- **PVI Durability Analysis Set:** CCI

CCI

5.2 Roll-In

- **Roll-In Analysis Set:** CCI

6 Sample Size Justification

CCI
CCI
I

CC

[Redacted]

CC

[Redacted]

- **Total Sample size:**

The sample size of this study is mainly driven by the hypothesis test for the primary safety endpoint. The total sample size for this study will be 135 evaluable subjects, CCI

[Redacted]

A total of 135 evaluable subjects will be included in the main study. Each of the four (4) subsets (NA, CT/MRA, EE and PVI durability) will target 30 subjects and will be integrated within the main study. Additionally, 30-50 subjects will be enrolled in the Roll-In analysis set.

CCI

[Redacted]

7 Statistical Analysis Methods

[figure not shown]
7.1 General Conventions

Descriptive summaries for continuous variables will include the number of observations with available data, along with the mean, standard deviation, median, 25% percentile, 75% percentile, minimum, and maximum values. As for categorical variables, the reporting will include the count and the corresponding percentage. Percentages will be based on the number of subjects with available data.

[figure not shown]
CCI

CCI

CCI

CCI

7.2 Disposition of Study Subjects

Subject disposition and accountability of the study subjects will be summarized descriptively for all enrolled subjects. The definition of disposition categories mentioned in section 19.5 of the study protocol will be used to categorize subjects.

7.3 Demographic and Baseline Characteristics

Subject demographics, medical history, previously failed and actively taking AADs utilization, and other baseline data will be summarized descriptively for all enrolled subjects. CCI

7.4 Endpoints and Associated Hypotheses

7.4.1 Primary Safety Endpoint

The primary safety endpoint is the occurrence of primary adverse events (PAEs) within 7 days of the index ablation procedure with the OMNYPULSE™ Catheter and TRUPULSE™ generator, except device or procedure related death, pulmonary vein (PV) stenosis, and atrio-esophageal fistula, which may also be considered as primary adverse event if occurring greater than one week (7 days) and less than or equal to 90 days post-procedure (section 7.4.1 in the Protocol). Cardiac Tamponade/Perforation occurring up to 30 days post AF ablation process procedure will also be considered a PAE (section 7.4.1 in the Protocol). The PAE rate will be compared against a performance goal of 12%.

The hypotheses to be tested for this evaluation are:

$$H_0: P_S \geq 0.12 \text{ vs. } H_A: P_S < 0.12,$$

where P_S denotes the rate of early onset primary adverse events.

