#### During the blanking period:

- Repeat procedures during the blanking period ( $\leq 90$  days post index ablation procedure) must be conducted with the investigational device, with or without focal touch-up, if the arrhythmia is due to PV triggers. ONLY after investigator deems unable to achieve PVI with the investigational device, a commercial and compatible BWI (RF) system can be used to complete the procedure (PVI only).
- If the arrhythmia is due to non-PV triggers and the subject is treated with a commercially available ablation catheter and generator, the subject will be excluded from the long-term effectiveness cohort.
- Procedures for newly CTI dependent flutter in the follow up period are not considered repeat procedures per CIP and will be treated with a commercially available ablation catheter and generator.

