### 13.5 Post-Ablation Follow-up Schedule

The subjects will be required to complete follow-up visits through 12 months post index ablation procedure. Follow-up will be done at 7 days (phone call or clinic visit), 1, 3, 6 and 12 months (clinic visit). Follow-up visits should be scheduled according to the following timeframes: 1 month (1M 23-37), 3 months (3M, day 76-104), 6 months (6M, day 166-194) and 12 months (12M, day 335-379). Follow-up visit schedule should be based on the date of the index ablation procedure and will not reset if subject undergoes a repeat AF ablation procedure.

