- Additional Assessments for **PVI Durability subset** subjects (non-SOC):
  - A repeat electro anatomical creation of a paced activation map and bipolar voltage map will be performed at 75 days (+/-15days) post index ablation procedure to verify isolation durability of the treated pulmonary vein during the index ablation procedure.
  - A BWI multi-electrode mapping catheter should be used for the remap procedure. It is **REQUIRED** to use the same mapping catheter that was used during the index ablation procedure.
  - If reconnections are identified in the remap procedure, additional ablations may be performed at the discretion of the investigator with the investigational ablation system. If the additional ablations cannot be achieved with the investigational system, a commercially approved and compatible BWI RF catheter and generator should be used.

- **Quality of life** via the Atrial Fibrillation Effect on Quality-of-Life (AFEQT™) questionnaire (non-SOC), at Month 3, 6 and 12. NOTE: Patient questionnaires will only be used in countries with validated languages.

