### 14.1.3 Primary Adverse Event

A **Primary Adverse Event** is an event listed in Table 5 which occurs within the first week (7days) following the study index ablation procedure.

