**Table 5: Primary Adverse Events**

Primary Adverse Event	Description / Criteria
Death 	Subject death directly related to the device or procedure and occurs at any time during or after the procedure.
Atrio-Esophageal Fistula 	Defined as a connection between the atrium and the lumen of the esophagus. Evidence supporting this diagnosis includes documentation of esophagus erosion combined with evidence of a fistulous connection to the atrium such as air emboli, an embolic event, or direct observation at the time of surgical repair. A CT or MRI scan is the most common method of documentation of an AEF.
Myocardial Infarction	
Presence of any one of the following criteria:
 
 
- Detection of ECG changes indicative of new ischemia (new ST-T changes or new Left Bundle Branch Block [LBBB]) that persist for more than 1 hour.
 
- Development of new pathological Q waves on ECG
 
- Imaging evidence of new loss of viable myocardium or new regional wall motion abnormality
 

Cardiac Tamponade  /Perforation	
The development of a significant pericardial effusion during or within 30 days of undergoing the index AF ablation procedure. A significant pericardial effusion is one that results in hemodynamic compromise, requires elective or urgent pericardiocentesis, or results in a 1 cm or more pericardial effusion as documented by echocardiography.
 
Cardiac tamponade/perforation should also be classified as:
 
 
• Early – diagnosed prior to discharge.
 
• Late – following initial discharge from the hospital.
 
 
Cardiac Tamponade/Perforation occurring within 30 days of the index ablation procedure will be considered a PAE for the study.

Thromboembolism	
Formation of a clot (thrombus) inside a blood vessel causing obstruction to blood flow accompanied by clinical symptoms. The thrombus can migrate (embolus) and obstruct distal vascular sites.
 
Diagnostic tests to help detect thromboembolisms may include but are not limited to angiography (pulmonary or distal), ventilation-perfusion (V/Q) scans, venography, Doppler ultrasonography, spiral CT, and echocardiography.
 
For the purpose of this study silent (asymptomatic) cerebral embolism will not be considered a PAE.

Primary Adverse Event	Description / Criteria

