Major Vascular Access Complication /Bleeding	
Major Vascular Access Complication: Development of a hematoma, an AV fistula or a pseudoaneurysm which requires intervention, such as surgical repair or transfusion, prolongs the hospital stay, or requires hospital admission.
 
Major Bleeding: Requires and/or treated with transfusion or results in a 20% or greater fall in hematocrit.

Pericarditis	Pericarditis should be considered a major complication following ablation if it results in an effusion that leads to hemodynamic compromise or requires pericardiocentesis, prolongs hospitalization by more than 48 hours, requires hospitalization, or persists for more than 30 days following the ablation procedure.
Heart Block	Impairment of AV conduction requiring intervention (e.g., temporary, or permanent pacemaker) due to iatrogenic cause (e.g., inappropriate energy application, traumatic maneuvering of catheter or other intracardiac devices)
Pulmonary Edema (Respiratory Insufficiency)	
Respiratory insufficiency resulting in pulmonary complications necessitating intubation or other significant intervention (including diuretics administered specifically for treating pulmonary edema or ICU hospitalization requiring oxygen administration but not intubation). Exclusion criteria include:
 
 
• Pneumonia – infiltrate, fever, and leukocytosis
 
• Acute Respiratory Distress Syndrome
 

Vagal Nerve Injury/ Gastroparesis	Injury to the vagal nerve that results in esophageal dysmotility or gastroparesis. Vagal nerve injury is considered to be a major complication if it requires or prolongs hospitalization  , or results in ongoing symptoms for more than 30 days following an ablation procedure.

 Device or procedure related death, atrio-esophageal fistula and pulmonary vein stenosis that occur greater than one week (7 days) and less than or equal to 90 days post-procedure are considered and analyzed as Primary AE.

 Hemodynamic compromise or instability is defined as Systolic blood pressure < 80 mmHg.

 Patients with non-focal global encephalopathy will not be reported as a stroke without unequivocal evidence based upon neuroimaging studies.

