7.11.2 Additional Safety Endpoints

The following analyses for the additional safety endpoints will be summarized descriptively in Safety, mITT, and Roll-In analysis sets as the total number of events, number of subjects with events, and percentage of subjects with events:

- Occurrence of Serious Adverse Device Effects (SADEs)
- Occurrence of Unanticipated (Serious) Adverse Device Effects (USADEs)

- Occurrence of Serious Adverse Events (SAEs) within 7 days (early-onset), 8-30 days (peri-procedural), and >30 days (late onset) of index ablation procedure
- Occurrence of non-serious adverse events (non-SAEs)

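### Complications of study-device re-ablation up to Day 90 are timed from the index procedure, so most cannot count as PAE-type events and, after a remap, every SAE is labelled late onset

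*SAP*

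**What the plan says.** **Safety windows.** SAP 7.4.1 sets the primary safety endpoint as the "occurrence of primary adverse events (PAEs) within 7 days of the index ablation procedure". Protocol 14.1.3 agrees: a PAE is a listed event "which occurs within the first week (7days) following the study index ablation procedure". Table 5 defines tamponade as "The development of a significant pericardial effusion during or within 30 days of undergoing the index AF ablation procedure". SAP 7.11.2 tabulates SAEs "within 7 days (early-onset), 8-30 days (peri-procedural), and >30 days (late onset) of index ablation procedure".

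Two windows are less clear. Table 5 extends related death, atrio-esophageal fistula and PV stenosis to events "that occur greater than one week (7 days) and less than or equal to 90 days post-procedure are considered and analyzed as Primary AE", without naming the index procedure. The 30-day tamponade rule in SAP 7.4.1 and in the footnote to Protocol 7.4.1 also omits the word index, whereas Table 5 includes it.

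**Second use of the study system.** Under Protocol 13.4, a blanking-period repeat (to Day 90) "must be conducted with the investigational device, with or without focal touch-up, if the arrhythmia is due to PV triggers". At the remap of the PVI durability subset, Protocol 13.5.2 says that "additional ablations may be performed at the discretion of the investigator with the investigational ablation system". Protocol 7.3.4 puts the remap at 75 days plus or minus 15. Protocol 13.5 adds that the visit schedule "will not reset if subject undergoes a repeat AF ablation procedure".

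**What is captured regardless.** Protocol 14.1.1 treats any complication of a re-ablation as an AE. SAP 7.11.2 counts SADEs, USADEs and non-serious AEs with no time window.

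**The concern.** The plan has two kinds of study-device procedure and one clock. An acute complication belongs in time to the procedure that caused it. Here a stroke on the day of a Day-75 study-device ablation is not a PAE, and the SAE table files it with events arising more than a month after treatment.

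The 3-month report goes into the CE-mark dossier. Its readers will take the PAE rate and the SAE timing table as the catheter's peri-procedural safety profile. For second uses, the table would move acute events into the late category. It would understate early risk and overstate late risk by whatever number of such events occurs. Adjudication follows the same line: the protocol summary gives the CEC the primary safety endpoint events, so no visible text sends it a PAE-type event that falls outside the endpoint only because of timing.

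**Working it through.** No figure in the plan is in dispute. The sample size of 135 is driven by the primary safety test, but the assumed rate and power behind it are redacted, so it cannot be reproduced, and this point does not need it. The check is day arithmetic on the stated windows.

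**Step 1. When the second exposure occurs.** Remap: 75 - 15 = Day 60 to 75 + 15 = Day 90. Blanking-period repeats: any day up to Day 90.

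**Step 2. Which PAE types can still count after a remap ablation on Day D (60 to 90).** The endpoint lists 14 types.

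| Types | Number | Window | Can an event after the remap ablation count? |
|---|---|---|---|
| Related death, atrio-esophageal fistula, PV stenosis | 3 | to Day 90, anchor not named | If index is meant: yes, for 90 - D days (30 at Day 60, 15 at Day 75, 0 at Day 90). If any procedure is meant: 90 days |
| Tamponade/perforation | 1 | 30 days | Table 5 (index): no, since 60 > 30. SAP 7.4.1 wording, if read as any ablation: yes, for 30 days |
| All others | 10 | 7 days from index | No, since 60 > 7 |

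Check: 3 + 1 + 10 = 14. Under Table 5 the excluded types number 1 + 10 = 11 of 14 (79%). Under the wider reading of the SAP tamponade text they number 10 of 14. The same tamponade after a Day-75 ablation is therefore outside the endpoint under one document and arguably inside it under the other.

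**Step 3. SAE onset bins.** A remap ablation is on Day 60 or later, and 60 > 30, so every SAE it causes falls in the late-onset bin, including one on the same day. Early repeats behave differently. After a Day-20 repeat, an SAE on Day 20 falls in the 8-30 day bin, and one starting on Day 31 (11 days after the repeat) falls in the late bin.

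**Step 4. How many procedures.** The documents fix only the number of planned remaps: 30 of 135, or 22%. At most 30 remap ablations with the study system are therefore possible in that subset, plus an unstated number of blanking-period repeats. As an illustration only, assume that 2-10% of 135 have a repeat and that 10-100% of the 30 are re-ablated:

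- low: 0.02 x 135 + 0.10 x 30 = 2.7 + 3.0 = 5.7 procedures
- high: 0.10 x 135 + 1.00 x 30 = 13.5 + 30 = 43.5 procedures

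With an assumed 3-12% of these followed by a PAE-type event outside the present windows, the expected count runs from 5.7 x 0.03 = 0.2 to 43.5 x 0.12 = 5.2. All three rates are assumptions. The range is too wide to be a finding; it shows only that the number need not be negligible.

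**The case against.** The best defence is that the endpoint is deliberately defined per index procedure, is tested against a goal built from composite complication rates in earlier trials (Protocol 5.3), and states its anchor openly. Nothing is hidden: AEs are collected from consent to study end (14.4.1), Table 4 marks them under unscheduled visits, and each is graded for relation to device and procedure. A device-related tamponade at a Day-75 re-ablation would appear as a SADE. On this view only a presentation choice is left. Most of that stands, and it is why the primary endpoint should stay as it is. It does not answer the timing label: a SADE count without a clock does not show that the event was acute, and the one table with a clock places it wrongly.

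A second objection is redaction. SAP 7.11.3 announces analyses of repeat ablations and the list is then blacked out; the general conventions and safety sensitivity analyses are also partly or wholly redacted, and the CEC charter and Safety Management Plan are not among the documents. This stands as a limit: absence can be claimed only for the visible text.

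Stronger readings that a reader might infer, and that the documents do not support:

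- *Every safety window runs from index.* SADEs, USADEs and non-serious AEs have no window, and the 90-day wording and the SAP tamponade wording name no anchor.
- *All re-ablation complications leave the endpoint.* Related death, fistula and PV stenosis to Day 90, and tamponade to Day 30, count whichever procedure caused them.
- *Device failures at a repeat go uncollected because Table 4 marks them only at index pre-discharge.* Protocol 14.4.4 requires all study-device failures to be reported within 72 hours, with no limit to the index procedure.
- *Re-ablated subjects go unobserved because visits do not reset.* Unscheduled visits have their own form, and AE and SAE reporting duties run throughout.

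**Conclusion.** The point holds as a gap in coverage and labelling in the descriptive safety analyses, not as an error in the primary test. For ablation with the study system at a Day 60-90 remap, 11 of 14 PAE types cannot count (10 if the SAP tamponade wording is read as any ablation). Three count for 30 to 0 further days if the 90-day window runs from index. All resulting SAEs are labelled late onset. For blanking-period repeats the late label applies only to SAEs starting after Day 30.

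These statements rest on the quoted windows and need no assumed rate. How many events are affected cannot be determined from the documents, and any probability of at least one missed event would rest wholly on assumed rates. A reader might also infer that the primary result could turn on one uncounted subject, because with 135 analysed the exact test passes at 8 subjects with events (upper bound 11.3%) and fails at 9 (12.3%). The arithmetic is right but does not bear on this point: such events lie outside an endpoint defined per index procedure, and the change proposed does not touch the test.

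**What to change.** Leave the primary endpoint, hypotheses and test unchanged.

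1. In SAP 7.11.2, add to both the 3-Month and the Final CSR a descriptive table of PAE-type events (Table 5 definitions, CEC-adjudicated) within the same 7-, 30- and 90-day windows after any procedure using the study system: index, blanking-period repeat or remap ablation. Use the analysis sets already named there and give the number of procedures as well as subjects. After a Day 60-90 ablation the 7-day window closes on Day 67-97, the 30-day window on Day 90-120 and the 90-day window on Day 150-180. The 3-Month CSR should therefore state how many procedures have completed each window, and the Final CSR should complete the table.
2. Tabulate SAEs and SADEs by days since the most recent study-device procedure, beside the existing bins from index.
3. State the anchor of the 30- and 90-day windows, and reconcile Table 5 with SAP 7.4.1 on tamponade.
4. If the redacted repeat-ablation analyses already contain items 1 or 2, a cross-reference from 7.11.2 is enough.

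The cost is a little extra tabulation and adjudication. Type I error and sample size are unaffected. The reported complication rate may look less favourable.
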